Methods: A proof of action repeated-measures study will be conducted in which healthy men and women (N=15) will be recruited to perform a series of balance and gait measures before using the foot device for a week and after the week of use. The following functional tasks will be performed at each time point: static balance on force plates (two-legged stance, one-legged stance and tandem stance), walking gait measures on an instrumented treadmill (at a preferred speed and a standardized speed) and walking measures on a pressure-sensor filled gait mat. For balance, the center of mass displacement, the variation about the displacement and the speed of the displacement will be calculated during post-processing. For gait, the ankle, knee and hip joint moments and joint excursion kinematics in the sagittal plane of motion will be calculated. The peak ground reaction force, the rate of impact loading and the impulses will be calculated during post-processing. A repeated measures analysis of variance will be used to determine whether significant improvements in the functional outcomes occurred. The one-week change scores in the functional task outcomes will be calculated, and effect sizes of the foot

device on the key functional variables will be determined using Cohen's *d*. Significance will be established at $p < 0.05$.

Application: The findings from this study will improve our understanding of foot device impact on functional performance in people without pre-existing conditions, and will help us create effect sizes for subsequent larger trials.

Introduction

The human foot is the initial point of contact between the body and the environment, and is a critical point to provide sensory information to the central nervous system during dynamic and static tasks (Nurse et al. 2005). The specialized mechanoreceptors of the plantar surface of the foot influence balance, dynamic stability and motion correction strategies. Thus, cutaneous stimulation of the nerves in the foot can dramatically change the motion of the lower extremity. For example, during walking and running, stimulation of the foot nerves (through varied experimental methods) can directly impact α -motorneuron output to the leg musculature (Nurse et al. 2005; Zehr et al. 1997). This output alters the kinematics of motion during gait.

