We seek to expand the understanding and application of the foot device concept to healthy people for injury prevention and performance enhancement. We will determine whether a different design of foot device can improve static balance and gait parameters. Medicine trends are moving toward self-management of healthy movement and preventative strategies to injury. More evidence is needed to determine whether the type of foot device we will test here has potential to improve balance, posture and stability – all of which promote healthy movement and reduce injury risk over the long-term. Here, a proof of action study will be performed to determine the effect size of the foot device use on functional task outcomes of balance and gait in healthy people.

Specific Aims

The Specific Aims of this study are to determine the effect of a foot device after one week of acclimation and use on functional variables of balance and gait. We will test the following hypotheses using the following specific aims:

1) *Determine the effect of an experimental foot device on static balance and center of mass displacement (sway) during standing.*

Hypothesis: Compared to the initial baseline measures, static balance will be improved as shown by reductions in the displacement of the center of mass, speed of motion of the center of mass and less trunk sway. We hypothesize that improvements in balance and sway will occur in two-legged stance, single-legged stance and in tandem stance.

2) *Determine the effect of an experimental foot device on walking gait temporalspatial parameters, ground reaction force patterns and joint forces, and relative foot pressure patterns.*

Hypothesis 2a: After one week, participants will demonstrate improvements in temporal spatial parameters (gait speed, stride width, swing time and single support time) compared to initial baseline measures. We also hypothesize that the rate of impact loading will be lower after one week of use.

Hypothesis 2b: We hypothesize that there will be a shift in foot pressure patterns from the typical pattern to that of pressures that indicate transfer of body weight over the heel, lateral metatarsals and hallux.

Methods

Study Design: This is a repeated-measures study in which participants will serve as their own control. Balance and gait measures will be collected during an initial visit and after one week of using the experimental foot device.

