Balance and Postural Sway Conditions: Each participant will perform three conditions of balance on the in-ground force plates (AMTI, Watertown MA). This measure is one of the most important variables in the study and was used to generate the sample size estimate. The three conditions will include two-foot stance, single foot stance and tandem balance stance. Following standardized instructions, participants will hold each position for 20-second intervals during which time force data will be captured at 1200 Hz. These collective measures will take roughly two minutes. This measurement technique is commonly used to assess postural stability and balance (Brown et al 2007; McKeon et al. 2012; Menz et al. 2017) and has demonstrated sensitivity to detecting change with shoe inserts that were designed to improve balance and gait (Menz et al. 2017). The images below show the three balance conditions:

A.

B.

C.

A. Two-foot stance: Participants will be asked to place their feet together and hold their arms at their sides. Participants will stand looking straight ahead and hold as still as possible.

B. Single foot balance: Participants will be asked to stand on the dominant foot and hold the other foot up, such that the knee creates a 90 degree angle. The participants will stand looking straight ahead and hold as still as possible.

C. Tandem stance: Participants will be asked to place their dominant foot forward and place the toes of their other foot to the heel of the dominant foot. The participants will stand looking straight ahead and hold as still as possible.

Once the data are collected, calculations of center of mass displacement (in cm), the variability of displacement and area (cm^2), and the peak speed of displacement (cm per second) will be determined. These values will provide insight about direction of sway and how quickly sway occurs during these three balance conditions.

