Because there are no directly comparable data from which to construct a matched sample size estimate, we have used the study with the closest match in aims and population (Hamlyn et al. 2012). For the matched pairs design, this study would require a sample size of 14 people to achieve a power of 80% and a level of significance of 5% (two sided), for detecting a mean of the differences of 17 cm² of postural sway area between pairs, assuming the standard deviation of the differences to be 20 cm².

Analysis for the Specific Aims:

Descriptive statistics (means and standard deviations for continuous variables, frequencies and percents for categorical variables) will be calculated on all study variables and demographics. Normality of the data will first be confirmed using Shapiro-Wilk tests.

Aim 1: Determine the effect of an experimental foot device on static balance and center of mass displacement (sway) during standing. We will use repeated measures analysis of variance (ANOVA) to determine whether significant improvements in the functional outcomes occurred. The dependent variables will be the key functional task outcomes for balance (center of mass displacement, variability of displacement and area, and the peak speed of displacement) and the independent variable will be time (initial assessment, week one). Covariates to the models will be body weight and sex. The one-week change scores in the functional task outcomes will be calculated, and effect sizes of the foot device will be determined using Cohen's *d*. For these described statistical tests an α level of 0.05 will be established as significant.

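### Balance speed is defined only as a peak; filtered mean sway speed from the same 20-second records would be a more repeatable outcome

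*Combined protocol and SAP*

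**What the plan says.** - **Balance and Postural Sway Conditions.** On recording: "participants will hold each position for 20-second intervals during which time force data will be captured at 1200 Hz". The speed measure to be derived is a maximum: "the peak speed of displacement (cm per second) will be determined".
- **Statistics, Aim 1.** The dependent variables are "center of mass displacement, variability of displacement and area, and the peak speed of displacement". No mean speed is listed.
- **Specific Aims, Hypothesis 1.** Improvement is to show as reductions in, among others, "speed of motion of the center of mass and less trunk sway". It says neither peak nor mean.
- **Abstract, Methods.** "the speed of the displacement will be calculated during post-processing", again without the word peak and without a processing method.
- **Closing Statistics description.** It lists antero-posterior and medial-lateral sway and sway velocities by direction, without saying peak or mean.

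For the stance data, the documents do not state a filter, cut-off, down-sampling or differentiation method. They do not say whether center of mass comes from markers, integrated force or center of pressure. Holds per stance are also not stated; the only guide is "These collective measures will take roughly two minutes" for all three stances.

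**The concern.** The maximum of a record is one value at one instant, and a brief foot adjustment can set it. The mean uses the whole record. The hypothesis asks whether people sway more slowly, and a whole-record average answers that more directly. With 15 participants, a summary with needless sampling error lowers the chance of seeing a real change. It also makes Cohen's *d* less reliable, and the Abstract intends the effect sizes to inform larger trials.

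A second worry is conditional. Differencing a signal sampled at 1200 Hz amplifies measurement noise, and a maximum then picks out the largest noise excursion. If that is how speed is computed, the peak could respond little to a true change in sway.

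**Working it through.** **1. The plan's own figure.** The documents give no SD, precision or power for speed. The sample size of 14 rests on sway area: 17/20 = 0.85 SD of the paired differences, two-sided 5%. A paired t-test (noncentral t) gives power of 80.3% at 13, 83.6% at 14 and 86.4% at 15. That figure is sound to within one person but says nothing about speed.

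**2. Peak against mean, both filtered.** Inputs from the plan: 20 s at 1200 Hz, so 20 × 1200 = 24,000 samples. Assumed inputs, not in the documents: two-axis low-frequency sway with SD 0.5 or 0.8 cm, white position noise with SD 0.0001 to 0.03 cm, and a second-order 10 Hz Butterworth filter run forward and backward. Simulating 60 people with two holds each gave:

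| | Filtered peak | Filtered mean |
|---|---|---|
| Within-person CV | 9.9–13.1% | 4.9–7.5% |
| Test-retest correlation | 0.69–0.89 | 0.89–0.97 |

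The mean was the more repeatable in every pairing. For a 20% sway reduction, the ratio of standardized paired effects (mean over peak) ran from 2.11/1.35 = 1.56 to 3.19/1.21 = 2.64. Over a wider set of sway models the CVs are about 10–15% for peak and 4–10% for mean.

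**3. What is left over one week.** Step 2 has no visit-to-visit variation. Take mid-range CVs of 11% (peak) and 5.5% (mean), and assume the same between-visit CV for both:

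- Between-visit CV 10%: √(10² + 11²) = 14.9% against √(10² + 5.5²) = 11.4%; SD ratio 1.3, variance ratio 221/130.25 = 1.7.
- Between-visit CV 20%: √(20² + 11²) = 22.8% against √(20² + 5.5²) = 20.7%; SD ratio 1.1, variance ratio 521/430.25 = 1.2.

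Without visit variation the SD ratio would be 11/5.5 = 2.

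**4. Noise, if an unfiltered 1200 Hz position signal is differenced.** Velocity noise SD per axis = √2 × 1200 × σ = 1,697σ per second. The expected two-axis noise-only peak is about 1,697σ × √(2 ln 24,000) = 1,697σ × 4.49 = 7,622σ. The simulated noise-free peak is about 4 to 11 cm/s, so noise matches it at σ = 4/7,622 = 0.0005 cm to 11/7,622 = 0.0014 cm.

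| Assumed σ (cm) | Noise-only peak (cm/s) | Fall in raw peak for a 20% sway reduction (sway SD 0.5; 0.8 cm) |
|---|---|---|
| 0.0001 | 0.8 | 18%; 19% |
| 0.001 | 7.6 | 6%; 13% |
| 0.005 | 38 | 0.3%; 2.5% |
| 0.01 | 76 | 0.1%; 0.6% |

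A separate run with a 15% reduction shows the same pattern: the raw peak falls by about 13–15% at 0.0001 cm, 3–10% at 0.001 cm, and under about 1% from 0.005 cm upward. Where noise dominates, the raw peak's CV is only about 5–6%, because the noise maximum is itself stable. Low scatter would therefore not be reassuring.

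**The case against.** A reader might infer that the outcome as written is mostly noise. The documents do not support this. The 1200 Hz rate is stated for force data, while the outcome is center of mass, which a force plate does not record directly. Markers are applied before testing, and the marker system's frame rate is not given. With a marker-based or integrated-force center of mass, the differencing argument does not apply directly. The noise SD is undocumented, and the answer reverses within the range in step 4: at 0.0001 cm noise adds only about 2–9% to the peak.

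A reader might also infer that no smoothing is planned. The Abstract mentions post-processing. An unstated filter is missing detail, not a decision to analyze raw differences.

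A third tempting claim is that the mean carries one quarter of the variance. That follows from a twofold CV ratio within holds, omits visit-to-visit variation and depends on the sway model.

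Nor is it certain that only one hold per stance is used. Three 20-second holds take one minute of the roughly two allowed, so repeats are possible. Averaging several peaks would help, though each would still rest on one instant.

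Finally, peak speed captures brief fast corrections. The simulations shrink all sway in proportion, so both summaries respond equally. If the device mainly damped those corrections, the peak might respond more. This stands, and is the reason to keep peak speed as a descriptive measure. Speed is also one of several Aim 1 variables and does not drive the sample size.

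**Conclusion.** The point holds for the choice of summary. Peak is the only balance speed outcome defined, although neither Hypothesis 1 nor the closing description calls for a peak. Under assumed low-frequency sway, filtered mean speed from the same record is more repeatable: hold-to-hold CV about 4–10% against 10–15%. For the one-week change the advantage is smaller, about 1.1 to 1.3 in SD under the assumed between-visit CVs of step 3.

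Noise dominance is a possibility only. It requires differencing an unfiltered 1200 Hz position signal, and it depends on the noise SD: little effect at 0.0001 cm, a large one near 0.001 cm, and almost no remaining response at 0.005 cm or more. The sway amplitudes, noise levels and filter are all assumptions. This is a modest, inexpensive improvement in precision, not a defect that invalidates Aim 1.

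**What to change.** In Balance and Postural Sway Conditions and in the Aim 1 analysis, make mean sway speed the speed outcome: path length divided by 20 s, with antero-posterior and medial-lateral components, which also brings both sections into line with the closing Statistics description. State how stance center of mass is derived. Name one low-pass filter in advance (for example 10 Hz, zero-lag, the setting used in step 2) and apply it identically at both visits. Keep peak speed, from the filtered signal, as descriptive.

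The cost is wording and processing only, on the same records. The downside is that brief fast corrections weigh less in a mean. The closing description is in the past tense; if the records have already been processed, report both summaries and say when the mean was chosen.

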Walking Gait. Two types of gait tests will be used to comprehensively characterize the gait patterns, motion and foot pressures that occur during walking: a force-plated treadmill and a GaitRite® gait mat. First, kinematic and kinetic measures will be captured using 3-dimensional (3D) motion capture techniques. High-speed filming will also be used to record a video reference of each condition (Edgertronic Inc, San Jose, CA; frame rate=498 frames per second). Once completed, each participant will walk across a gait mat to obtain relative foot pressure patterns. The total time to complete all the gait tests is approximately 15-20 minutes.

3D Instrumented Motion Analysis on Force Plated Treadmill: To determine ground reaction forces (GRFs) during walking, dynamic assessments of these forces and force patterns

(kinetics) will be collected during a 10 second sample period with participants walking a self-selected speed and a standardized speed on a force-plated treadmill (AMTI, Watertown, MA USA). Each participant will first be acclimated to the treadmill, then allowed to walk for three minutes at a self-selected pace. Participants' walking motion (kinematics) will be captured by using a high-speed 7-camera optical motion analysis system (Motion Analysis Corp, Santa Rosa, CA, USA). Then participants will be asked to walk at standardized speed of (3.2 mph), a speed at which corresponds to an average preferred walking speed of healthy adults in the age range we will use here (Van Uden and Besser, 2004).

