Kinematics and kinetics will be derived from the marker data using standard rigid body mechanics equations implemented within commercially available software (Cole et al. 1993). During the last minute, a sample of walking data will be captured and written to disc for offline processing. The following measures will be obtained in the sagittal plane for the ankle, knee, hip and pelvis joint: joint angles at foot contact, peak angles at mid-stance and excursion (range of motion per joint). These data will be processed using Visual 3D software. The peak GRFs in each of the three planes (sagittal, frontal and transverse) will be determined. Knee moments and the rate of force development after foot contact will be calculated for each leg (DeLeva et al. 1996). Moments will be adjusted for body weight X height. The picture above left shows the instrumented treadmill setup. The vertical displacement of the center of mass (COM) will be calculated as the difference in the maximal and minimal vertical height of the estimated COM during an average gait cycle. The stance time was determined as the percent of the gait cycle during which the foot made contact with the treadmill. Cadence, COM vertical displacement, step length, step width will also be calculated.

GaitRite® Gait Mat Measures: Participants will be asked to walk across the 26' long gait mat and their self-selected speed to capture the foot pressure patterns. The pressures are color

mapped, where higher pressures are brighter reds and blues, where areas of low pressure are represented by grey or light blue. Temporalspatial parameters will also be captured (cadence, speed, step lengths, step width, toe out angle, stance and swing time and variability about these measures). A total of six trials will be

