Aim 2: Determine the effect of an experimental foot device on walking gait temporalspatial parameters, ground reaction force patterns and joint forces, and relative foot pressure patterns. Similar to Aim 1, repeated measures ANOVAs will be used to determine whether significant improvements in the dependent variables for walking gait occurred. The dependent variables will be the kinematics in sagittal plane, temporalspatial parameters, ground reaction forces, impact loading rate and foot pressure change. The independent variable will be time (initial assessment, week one). The one-week change scores in the functional task outcomes will be calculated, and effect sizes of the foot device will be determined using Cohen's *d*. To determine whether any statistically significant shifts in the peak pressures on the plantar surface occurred, Chi Square (χ^2) tests will be used. An α level of 0.05 will be established as significant.

Data Management: Data will be collected and saved in Microsoft Excel®. The electronic files will be de-identified and saved on the departmental, firewalled encrypted server. Data will be reviewed before analysis and cleaned to ensure that all numbers are within expected limits. Once data collection is complete, statistical analyses will be performed using the Statistical Package for the Social Sciences (SPSS version 24; IBM Chicago, IL).

Possible Discomforts and Risks, Protections against Risks

There are minor potential risks and discomforts associated with this study. All precautions will be put into place to minimize these risks.

Foot Device and Study Measures. The risks to participating in this study are minimal. A potential discomfort may be related to wearing the foot device during the one week period. The devices are purposefully designed to stimulate the plantar surface of the foot and may feel

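### Treadmill forces rest on a 10-second sample of about 9 to 11 strides per leg; recording the whole last minute would cheaply reduce noise in the treadmill outcomes, by an amount the documents cannot fix

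*Combined protocol and SAP*

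**What the plan says.** The section on 3D instrumented motion analysis says that ground reaction forces "will be collected during a 10 second sample period with participants walking a self-selected speed and a standardized speed on a force-plated treadmill". It describes the walking at the participant's own pace as follows: "Each participant will first be acclimated to the treadmill, then allowed to walk for three minutes at a self-selected pace". A bout at 3.2 mph comes next, with no duration given. Capture is placed late in the walk: "During the last minute, a sample of walking data will be captured and written to disc for offline processing".

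The sentence on motion capture gives no sample length: "Participants' walking motion (kinematics) will be captured by using a high-speed 7-camera optical motion analysis system". The section gives no reason for 10 seconds and no minimum number of strides. Its only averaging rule is that the vertical displacement of the centre of mass is taken over an average gait cycle.

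The Aim 2 analysis draws on both the treadmill and the gait mat: "The dependent variables will be the kinematics in sagittal plane, temporalspatial parameters, ground reaction forces, impact loading rate and foot pressure change". Foot pressure comes from the mat, averaged over six passes. The mat also supplies its own spatial and timing measures: "Temporalspatial parameters will also be captured (cadence, speed, step lengths, step width, toe out angle, stance and swing time and variability about these measures".

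**The concern.** Each participant is measured at two single visits a week apart, and the analysis rests on the difference. A visit mean built from few strides carries stride-to-stride noise, and the noise from both visits enters the change score. With 15 participants, that widens the interval around the effect sizes the study is meant to supply for later trials. If Cohen's d is standardised by the SD of the change, it also pulls d towards zero. Hypothesis 2a names the rate of impact loading, which is a treadmill outcome.

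At the self-selected pace, most of a minute that is already being walked appears not to be recorded. The plan is more generous with the gait mat: six passes of 26 feet cover 6 × 26 × 0.3048 = 47.5 m. That is at most about 30 to 37 strides per leg at the stride lengths assumed below, or roughly three times the treadmill sample.

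**Working it through.** **The plan's own figure.** The only power calculation is for sway area: mean difference 17 cm², SD of differences 20 cm², two-sided 5%, 80% power, n = 14. With d = 17/20 = 0.85, a paired t-test (noncentral t) needs 13 people (power 80.3%), and 14 give 83.6%. The stated 14 is reproduced to within one person. It does not involve the treadmill sample, so nothing below changes it.

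**Strides in the sample.** From the plan: 3.2 mph and 10 seconds. Assumed: step length 0.65 to 0.80 m, so stride length 1.3 to 1.6 m.
- Speed: 3.2 × 0.44704 = 1.4305 m/s.
- Strides per leg in 10 s: 14.305/1.6 = 8.9 to 14.305/1.3 = 11.0.
- Strides per leg in 60 s: 85.83/1.6 = 53.6 to 85.83/1.3 = 66.0.
- Cross-check by an assumed cadence of 100 to 130 steps per minute: 8.3 to 10.8 strides per leg in 10 s.

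**Effect on the change score.** Let sb be the visit-to-visit SD, sw the stride-to-stride SD, r = sw/sb, and n the strides averaged per visit. Then

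SD(change) = √[2(sb² + sw²/n)].

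With independent strides, moving from 9 to 55 strides multiplies this SD by √[(1 + r²/55)/(1 + r²/9)]. The documents give no value for r, so a range is assumed. The last column is the inverse square of the SD ratio, minus one.

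| r | SD ratio | Fall in SD of change | Equivalent extra participants |
|---|---|---|---|
| 0.5 | 0.989 | 1% | 2% |
| 1 | 0.957 | 4% | 9% |
| 1.5 | 0.913 | 9% | 20% |
| 2 | 0.862 | 14% | 35% |

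**In terms of power.** Take 10 against 60 strides, N = 15, a two-sided 5% paired t-test, and a treadmill outcome with a standardised change of 0.78 (power 80.2%). Power rises to 81.0%, 83.2%, 86.2% and 89.5% for the four ratios. For a standardised change of 0.5 (power 43.8%) it rises to 44.5%, 46.7%, 50.0% and 54.2%.

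**Correlated strides.** Under first-order autoregressive correlation of 0.5 (assumed), each visit mean is worth fewer independent strides at either length, so stride noise is a larger share of the total. For 9 against 55 strides at the same four ratios, the SD of the change falls by about 3%, 9%, 17% and 25%. Short-range correlation therefore increases the gain. Slow drift that does not average out within a minute would reduce it.

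**The case against.** The strongest reply is that nothing here is an error. The 10 seconds and the last minute are compatible, since a 10-second sample can lie within that minute. No stated calculation depends on the treadmill sample. More strides do nothing for day-to-day variation or for markers re-placed at the second visit. If those dominate, the gain is 1 to 4% of an SD and a few points of power at most. All of this stands, and it is why the point is an inexpensive improvement and no more.

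A reader might also infer stronger claims that the documents do not support:
- **That a full minute is already walked at both speeds, so the change costs participants nothing.** Three minutes is stated only for the self-selected pace. The length of the 3.2 mph bout is not given.
- **That kinematics are stated to use 10 seconds.** The figure is attached to forces. Joint moments need simultaneous force and marker data, so a shared sample is a sensible inference, but it is not in the text.
- **That all Aim 2 outcomes would gain.** Foot pressure (Hypothesis 2b) and the mat's spatial and timing measures do not depend on the treadmill sample. Among the explicit Aim 2 hypotheses, only loading rate clearly does.
- **That the study is shown to be underpowered for loading rate.** The documents give neither an expected change nor any SD for it.

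**Conclusion.** The point holds as a low-cost improvement of minor weight. A 10-second force sample gives about 9 to 11 strides per leg at 3.2 mph, and a full minute gives about 54 to 66. The change lowers stride-sampling noise in the treadmill outcomes only: peak ground reaction forces, loading rate, knee moments, joint angles and the treadmill's own spatial measures.

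Under the variance model used here the direction is certain, but the size is not. It rests on the assumed ratio of stride-to-stride to visit-to-visit SD, and the percentages for kinematics and moments further assume that they share the 10-second sample.

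**What to change.** In the section on 3D instrumented motion analysis:
- State the capture length separately for forces and for kinematics, at each speed.
- At the self-selected pace, record the full last minute.
- At 3.2 mph, state how long participants walk and record as much of the last minute as is walked.
- Use the same capture length at both visits, and average all complete strides per leg.

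The cost is protocol wording, disc space and extra processing time for staff. At the self-selected pace no further walking is needed. At 3.2 mph, a full minute of data may need up to about one extra minute of walking per visit, set against the plan's own estimate: "The total time to complete all the gait tests is approximately 15-20 minutes".

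### No outcome is called primary: the study is sized on sway area with no stance named, and every functional outcome is tested at an unadjusted 0.05 with no exploratory label

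*Combined protocol and SAP*

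**What the plan says.** The plan's statements, by section:

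- **Sample size.** Fourteen people are required for 80% power at two-sided 5%, for "detecting a mean of the differences of 17 cm² of postural sway area between pairs", assuming an SD of the differences of 20 cm². No stance is given.
- **Balance and Postural Sway Conditions.** Of the balance measure: "This measure is one of the most important variables in the study and was used to generate the sample size estimate". It is taken in three positions: "The three conditions will include two-foot stance, single foot stance and tandem balance stance". Area, in cm², is among the quantities to be calculated.
- **Specific Aims, Aim 1 hypothesis.** The expected effects are "reductions in the displacement of the center of mass, speed of motion of the center of mass and less trunk sway", and "improvements in balance and sway will occur in two-legged stance, single-legged stance and in tandem stance". Sway area is not named.
- **Analysis for the Specific Aims, Aim 1.** The dependent variables are "center of mass displacement, variability of displacement and area, and the peak speed of displacement", unranked, with time as the independent variable and a 0.05 level.
- **Analysis for the Specific Aims, Aim 2.** "repeated measures ANOVAs will be used to determine whether significant improvements in the dependent variables for walking gait occurred", again at 0.05.
- **Statistics description.** This short past-tense summary lists the main functional outcomes. For balance it gives directional sway and sway velocities, not area. It applies 0.05 to all tests.
- **Abstract, Application.** The findings "will help us create effect sizes for subsequent larger trials".

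None of these sections contains a primary outcome, a hierarchy, an exploratory label, a multiplicity statement or a rule for what would count as improvement.

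**The concern.** Sway area leads by implication, because N rests on it. Implication does not choose a stance, however, and the hypothesis and the closing summary point to other balance measures. A reader who sees one significant result among many cannot tell whether it is the result the sample size was meant to support.

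Both the false-positive risk and the power depend on a rule the plan leaves open. If any significant test may be put forward as proof of action, the risk exceeds 5%. If the hypothesis is read as requiring improvement in all three stances, the risk is very small but power falls below the stated 80% at low to moderate correlation.

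**Working it through.** **1. The plan's own sample size.** Inputs from Sample size: mean difference 17 cm², SD of differences 20 cm², two-sided 0.05, power 80%. The standardised paired effect is 17/20 = 0.85.

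- Normal approximation: ((1.960 + 0.842)/0.85)² = 10.9, so 11. Adding the small-sample term 1.960²/2 gives 12.8, so 13.
- Exact paired t-test (noncentral t): n = 13 gives 80.3%, n = 14 gives 83.6%, n = 15 gives 86.4%.
- With error df of n − 3, to allow for the two Aim 1 covariates, the smallest n is exactly 14.

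The stated 14 is reproduced to within one person. The arithmetic is sound; what is undefined is the outcome it applies to. The remaining steps ignore covariates.

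**2. If any one significant test counts (assumed rule), with no true effect.** For m independent tests, P(at least one p<0.05) = 1 − 0.95^m. In the favourable direction only, it is 1 − 0.975^m.

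- m = 3 (sway area in three stances): 1 − 0.95³ = 14.3%; favourable 1 − 0.975³ = 7.3%.
- m = 9 and m = 12 (three or four measures × three stances): 37.0% and 46.0%; favourable 20.4% and 26.2%.

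Change scores within a person are correlated, and the documents give no correlations. Simulating equicorrelated paired t-tests at n = 15 gives, as any direction (favourable):

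| Tests | Independent | Correlation 0.7 | Correlation 0.9 |
|---|---|---|---|
| 3 | 14% (7%) | 11% (5.5%) | 9% (4%) |
| 9–12 | 37–46% (20–26%) | 21–25% (11–12%) | 13–14% (6–7%) |

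One test alone gives 5% (2.5%). The count of 9–12 is an assumption, because the Aim 1 text does not say whether stances are analysed separately or together. The independent column is a ceiling: all measures in a stance come from the same 20-second recording.

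**3. If all three stances must improve (assumed rule).** Take 17/20 to hold in each stance, which the documents do not say. Joint power at n = 15 is 0.864³ = 64.5% if independent. By simulation it is 68%, 71% and 75% at correlations 0.3, 0.5 and 0.7. One stance alone has 86.4%. With no true effect, the chance that all three favour the device is below 0.4% over the same correlations.

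**4. Outcome lists side by side.** Area is in the balance measurement section and in the Aim 1 analysis list. It is not named in the Aim 1 hypothesis or in the Statistics description. The outcome that justifies N is thus missing from the statement of what is expected and from the summary of what was analysed.

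**The case against.** The best defence is the study's purpose. It is a single-group proof-of-action study in 15 healthy people, meant to produce effect sizes, with no stated go/no-go decision. For that purpose unadjusted p-values are acceptable, and change scores and Cohen's d are already planned for the functional outcomes regardless of p. This stands, and it makes the multiplicity part a labelling gap. It does not remove the gap, because the plan states directional hypotheses and tests for significant improvement without calling the tests exploratory.

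A reader might infer more than the documents support:

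- *That the plan's error rate is 37–46%.* It is not. Both success rules, the test count and the correlations are assumptions, and independence is implausible for measures sharing a recording.
- *That sway area was left out of the analysis.* It is in two of the four lists, and the hypothesis's reference to trunk sway may loosely cover it. The Statistics description is brief, has an unclosed bracket and does not say that it replaces the Aim 1 list.
- *That every outcome is tested.* Soreness and pain are reported as daily means; the point concerns the functional outcomes.
- *That the reported effect sizes will be inflated.* This follows only if results are highlighted because they were significant, which the plan does not propose. If they were, significant favourable estimates of d at n = 15 would average about 0.74, 0.79 and 0.97 for true d of 0.3, 0.5 and 0.85. The first two true values are assumed; the last is the plan's own, where the average over all estimates is already about 0.90.

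**Conclusion.** The point holds and should be fixed. The firm part needs no assumption: no outcome is called primary, the sizing outcome has no stance, two of the four outcome lists do not name it, and the 0.05 tests carry neither a hierarchy nor an exploratory label.

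The size is illustrative. For sway area in three stances, an any-one-counts reading gives about 9–14% in place of 5% for correlations from 0.9 down to 0. An all-three reading lowers power from 86% to about 65–75% for correlations 0 to 0.7, even with 17/20 in every stance. The figures show how much depends on an unstated rule; they do not measure the plan's actual error rate. The sample size need not change, provided 17/20 applies to the stance chosen.

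**What to change.** - **Sample size and Aim 1 analysis:** designate sway area in one named stance, the one the 17 and 20 cm² figures describe, as the single primary outcome at two-sided 0.05. If the figures do not describe a single stance, choose one without reference to the results and restate the power as conditional on 17/20 holding there.
- **Other outcomes:** state that the other two stances and all other Aim 1 and Aim 2 outcomes are secondary or exploratory, with unadjusted p-values that do not by themselves establish proof of action. Add a 95% CI to the planned change scores and Cohen's d, and report every outcome whatever its p-value.
- **Aim 1 hypothesis:** name sway area.
- **Statistics description:** reconcile it with the Aim 1 analysis. If area was analysed, list it. If it was not, disclose that as a deviation and do not add it to the record.
- **If the analysis is already done,** as the past tense suggests, also disclose that no primary outcome was prespecified.

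The cost is wording and reporting; visits, measurements and N = 15 do not change. Power for the primary outcome is 86% at N = 15 (84% at 14) if 17/20 holds for the chosen stance. The downside is that fewer outcomes can be presented as confirmed.
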